10.6 Duration of Follow up

Patients will be followed for any medical issues for a minimum of **8 weeks (6 months** is recommended) after removal from study or until death, whichever occurs first. Patients removed from study for unacceptable adverse events will be followed until resolution or stabilization of the adverse event. In addition patients will be followed \leq **every 1-3 months for survival until 5 years post treatment or until death**, whichever occurs first. Information on progression (as defined in this protocol) or death will be collected even if the patient has been removed from the study previously.

11 Statistical methods and data analysis

This phase IIa open label, proof-of-concept trial, that will be a arm study across several centers through the University of Chicago Personalized Cancer Care Consortium (PCCC) in which all eligible patients with histologically-confirmed recurrent/metastatic HNSCC and FGFR alteration will receive BGJ398 (infigratinib) at 125 mg PO daily.

20 patients will be enrolled on the study. Accrual of 20 patients is estimated to occur over 18-24 months.

Primary objective will be to assess efficacy of BGJ398 (infigratinib) in FGFR altered HNSCC (regardless of HPV status) using objective response rate (e.g. complete and partial response per RECIST 1.1 measurement).

11.1 Sample size calculation

Based on TCGA and our U Chicago cohort, FGFR2-3 mutations are estimated to occur in 5-8% of HPV (-) HNC and 10-15% of HPV (+) HNC. High level FGFR1 amplification (defined as copy number ≥ 4) is estimated to occur in 7-10% of HPV (-) HNC. FGFR3-TACC3 translocation is estimated to occur in 3-5% of either HPV (+) or HPV (-) head and neck cancers (in TCGA two TACC3-FGFR3 translocations occurred in HPV (+) HNC). It is expected that FGFR aberration will be mutually exclusive. The primary endpoint will be objective response rate (ORR; complete or partial response) in each of the two treatment arms (HPV(+) and HPV(-)).

With a Simon Two Stage Design (Minimax), a preset one-sided alpha level of 0.1 and power of 80%, we determined the minimum sample size required to detect the hypothesized response rate of 21% for BGJ398 (infigratinib) in each Cohort: A sample of 20 FGFR alteration (+) patients will be large enough to detect a response rate of 20% for BGJ398 (infigratinib) compared to a null response rate of 5% (Williamson et al. 2010, de Souza et al 2012) with 80% power and one-sided type I error rate of 0.10.

An interim analysis for futility will be conducted after 11 response evaluable patients without interruption of enrollment. If 0/11 responses are seen, the study will be stopped prematurely for futility. If at least one response is seen, an additional 9 patients will be enrolled. The results of the study will be deemed negative if ≤ 2 responses are seen in 20 patients.

Response rate of BGJ398 (infigratinib) in FGFR subgroups (as defined by certain genetic changes in FGFR1-3) will be reported if relevant as the grouping of genetic aberration as well as the size each group may not be sufficient for statistical analysis. The following grouping is suggested, but may be adapted as new information becomes available:

1. FGFR3 translocations
2. Other FGFR translocations
3. FGFR1 amplification
4. FGFR1 mutations
5. FGFR2 mutations
6. FGFR3 mutations
7. Other rare FGFR aberrations such as FGFR2 amplification, or FGFR3 amplification.

Kaplan-Meier estimates and 90% confidence intervals, using Greenwood's standard error estimate, will be tabulated at planned imaging intervals for progression-free survival (at 8 weeks, 16 weeks, 24 weeks, and every 8 weeks thereafter). Also, median PFS and 90% CI will be determined. We will perform similar analysis for Overall survival (OS) for up to 5 years.

We will report on duration of response and duration of stable disease and may consider a landmark analysis in responders versus non-responders.

12 Ethical considerations and administrative procedures

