4.7 Rationale for the study design

Based on the TCGA and our University of Chicago HNC cohort:

- FGFR2-3 mutations are estimated to occur in 5-8% of HPV (-) HNC and 10-15% of HPV (+) HNC.
- FGFR1 amplification is estimated to occur in 7-10% of HPV (-) HNC.
- FGFR3-TACC3 translocation is estimated to occur in 3-5% of either HPV (+) or HPV (-) head and neck cancers (in TCGA two TACC3-FGFR3 translocations occurred in HPV (+) HNC).
- Other translocations of FGFR genes as well as amplification of FGFR2/3 have been described to be oncogenic in other cancer types but based on absence in the TCGA HNC and Chicago HNC genomics cohort (CHGC) datasets to be rare in HNC.

The primary endpoint will be: **objective response rate** (ORR; complete or partial response).

With a **Simon Two Stage Design**, a preset **alpha level of 0.1** and **power of 80%**, we determined the minimum sample size required to detect the hypothesized response rate of 21% for BGJ398 (infigratinib): A sample of 20 FGFR altered patients will be large enough to detect a response rate of $\geq 21\%$ for BGJ398 (infigratinib) compared to a null response rate of 5% (Williamson et al. 2010) with 80% power and one-sided type I error rate of 0.10.

An interim analysis for futility will be conducted after 11 evaluable patients have been enrolled without interruption of enrollment. If 0/11 responses are seen, the study will be stopped prematurely for futility.

If at least one response is seen, an additional 9 patients will be enrolled. The results will be deemed negative (i.e., the 21% alternative will be rejected) if ≤ 2 responses are seen in 20 patients.

5 Population

Study population must meet both criteria below.

- A. Patients with recurrent/metastatic head and neck squamous cell carcinoma (HNSCC) not amenable to curative intent therapy (palliative treatment intent).
- B. Must harbor an FGFR genetic alterations (FGFR1-3 translocated, mutated, or amplified squamous cell carcinoma of the head and neck).

Enrollment target: N=20 patients. We estimate to have at least 3-5 patients with repeat tumor biopsies (mandatory for responders who subsequently demonstrate disease progression). All patients must have tumor material available for biomarker evaluation or confirmed FGFR1-3 translocated, mutated, or amplified squamous cell carcinoma of the head and neck.

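### Section 11.1 claims 80% power at a 20% response rate, but the stated 0/11, 2/20 design has 77.1% power there and reaches 80% only at the 21% given elsewhere

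*Combined protocol and SAP*

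**What the plan says.** Section 11.1 (Sample size calculation) specifies the design as "With a Simon Two Stage Design (Minimax), a preset one-sided alpha level of 0.1 and power of 80"%. It says of the target that "we determined the minimum sample size required to detect the hypothesized response rate of 21% for BGJ398 (infigratinib) in each Cohort". The same sentence then continues after a colon: "A sample of 20 FGFR alteration (+) patients will be large enough to detect a response rate of 20% for BGJ398 (infigratinib"). For that 20% it sets the null at 5%, citing two studies, and claims 80% power at a one-sided error rate of 0.10.

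Section 4.7 (Rationale for the study design) describes the same design with only one alternative. It refers to "the minimum sample size required to detect the hypothesized response rate of 21% for BGJ398 (infigratinib"), gives the detectable rate as at least 21%, and words the final decision the same way: "The results will be deemed negative (i.e., the 21% alternative will be rejected") when 2 or fewer responses are seen in 20 patients.

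The two sections agree on the rule itself: an interim look after 11 evaluable patients, a stop at 0 of 11, 9 more patients if there is at least one response, and a negative result at 2 or fewer of 20.

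**The concern.** The power claim in Section 11.1 is attached to 20%, while the first half of that sentence and all of Section 4.7 give 21%. With 20 patients and a final cut-off of 2 responses, one percentage point in the target moves the power by about three points, so both rates cannot go with 80%.

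The trial's conclusion is a test of one alternative against a 5% null, and Section 4.1.1 sends the reader to Section 11 for the statistical considerations. Someone who checks the design from Section 11.1 will not be able to reproduce the stated power. Someone who reports from it may cite the wrong alternative.

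**Working it through.** **Inputs.** Null rate 5%, one-sided alpha 0.10, target power 80% (Sections 4.7 and 11.1). Stage 1: n1 = 11, stop if 0 responses. Stage 2: 9 more patients, N = 20, negative if 2 or fewer responses (both sections). Alternative: 21% (Section 4.7 and the first half of the sentence in Section 11.1) or 20% (second half of that sentence).

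**Formula.** The trial is positive if there is at least one response in the first 11 patients and at least 3 in all 20:

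P(positive | p) = Σ over x = 1 to 11 of P(X1 = x) · P(X2 ≥ 3 − x), with X1 ~ Bin(11, p) and X2 ~ Bin(9, p).

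An equivalent form is easier to check by hand. Take the single-stage probability of 3 or more in 20, and subtract the cases lost to the futility stop:

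P(positive | p) = P(Bin(20, p) ≥ 3) − (1 − p)^11 · P(Bin(9, p) ≥ 3).

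**Results.**

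| True rate p | P(Bin(20, p) ≥ 3) | (1 − p)^11 | P(Bin(9, p) ≥ 3) | P(positive) |
|---|---|---|---|---|
| 5% | 0.0755 | 0.5688 | 0.0084 | 0.0755 − 0.0048 = **0.0707** |
| 20% | 0.7939 | 0.0859 | 0.2618 | 0.7939 − 0.0225 = **0.7714** |
| 21% | 0.8230 | 0.0748 | 0.2885 | 0.8230 − 0.0216 = **0.8014** |

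The plan's 80% is reproduced at 21% and not at 20%. Solving P(positive | p) = 0.80 gives p = 0.2095. The type I error of 0.0707 meets the 0.10 limit.

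**Which rate the design was built for.** An exhaustive search over Simon rules with alpha ≤ 0.10 and power ≥ 80% gives:

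- 5% versus 21%: the smallest N is 20. Among rules of that size, the lowest expected size under the null is at 0/11, 2/20, where it is 11 + (1 − 0.5688) × 9 = 14.9. This is the rule printed in the plan.
- 5% versus 20%: the smallest N is 21, with 0/12, 2/21 (power 80.3%, alpha 0.080). Both the first-stage size and the total differ from the plan.

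**Could another 20-patient rule support the 20% claim?** No. Over all Simon rules with N = 20 and alpha ≤ 0.10, the highest power at 20% is 79.4%.

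**The case against.** The best defence of the text is that the futility stop barely matters. If it is ignored, the rule of 3 or more in 20 has 79.4% power at a rate of 20%, which rounds to 79% and is close to 80%. But both sections say the trial stops at 0 of 11. The remark that enrollment is not interrupted means accrual is not paused for the interim analysis; it does not cancel the stop. The futility stop belongs in the power, and 77.1% does not round to 80%.

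A second objection is that the matter is editorial. The 20% is contradicted within its own sentence and three times in Section 4.7, so a careful reader can recover the intended value, and no stage size or boundary depends on it. This stands, and it is why the point is minor.

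A third objection limits how far the design can be called sound. Section 11.1 also speaks of each cohort, and of a primary endpoint in each HPV arm. Section 4.1.1 gives 15 HPV-positive and 15 HPV-negative patients, while other sections give 20 in total. In addition, Section 7.3.1 counts only patients with a post-baseline scan as evaluable for response. The margin over 80% at 21% is 0.14 percentage points, and no Simon rule with fewer than 20 patients reaches 80% at 21% within alpha 0.10. The reassurance about sample size and power therefore holds for one cohort of 20 evaluable patients and no further. These are separate matters and do not change the finding on 20% versus 21%.

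**Conclusion.** The point holds, at minor severity. As written, the claim of 80% power at 20% in Section 11.1 is wrong by 2.9 percentage points (77.1%), and it conflicts with the 21% in the same sentence and in Section 4.7. The printed rule is the minimax design for 5% versus 21%, with 80.1% power and type I error 0.071, so the 20% is most likely a slip for 21%. The calculation assumes that the 0/11 stop is applied as stated and that the final rule is applied to a single cohort of 20 evaluable patients. On those terms the sample size, stage sizes, boundaries and alpha control are not in error.

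**What to change.** In the second half of the sample-size sentence in Section 11.1, replace 20% with 21%, so that it agrees with the first half and with Section 4.7. If the 20% is deliberate, keep it, restate the power as 77%, and bring the other mentions of the target rate into line.

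The first option is a one-figure correction using a number already in the plan. It needs no new design decision, no more patients and no change to the interim or final boundary.

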12.1 Ethics and good clinical practice

This study must be carried out in compliance with the protocol and Good Clinical Practice, as described in:

1. ICH Harmonized Tripartite Guidelines for Good Clinical Practice 1996.
2. Directive 91/507/EEC, The Rules Governing Medicinal Products in the European Community.
3. US 21 Code of Federal Regulations dealing with clinical studies (including parts 50 and 56 concerning informed consent and IRB regulations).
4. Declaration of Helsinki, concerning medical research in humans (Recommendations Guiding Physicians in Biomedical Research Involving Human Subjects, Helsinki 1964, amended Tokyo 1975, Venice 1983, Hong Kong 1989, Somerset West 1996).

The investigator agrees, when signing the protocol, to adhere to the instructions and procedures described in it and thereby to adhere to the principles of Good Clinical Practice that it conforms to.

12.2 Discontinuation of the study

Novartis reserves the right to discontinue support for any study under the conditions specified in the clinical trial agreement.

12.3 Publication of results

Any formal presentation or publication of data from this trial may be published after review and comment by Novartis and prior to any outside submission. Novartis must receive copies of any intended communication in advance of publication (at least twenty-one working days for presentational materials and abstracts and thirty working days for manuscripts). These requirements acknowledge Novartis' responsibility to provide peer input regarding the scientific content and conclusions of such publications or presentations. Principal Investigation/Institution shall have the final authority to determine the scope and content of its publications, provided such authority shall be exercised with reasonable regard for the interests of Novartis and, in accord with the trial contract and shall not permit disclosure of Novartis confidential or proprietary information.

12.4 Disclosure and confidentiality

The investigator agrees to keep all information provided by Novartis in strict confidence and to request similar confidentiality from his/her staff and the IRB/IEC/REB. Study documents provided by Novartis (investigators' brochures and other material) will be stored appropriately to ensure their confidentiality. The information provided by Novartis to the investigator may not be disclosed to others without direct written authorization from Novartis, except to the extent necessary to obtain informed consent from patients who wish to participate in the trial.

12.5 Declaration of Helsinki

The investigator must conduct the trial in accordance with the principles of the Declaration of Helsinki. Copies of the Declaration of Helsinki and amendments will be provided upon request or can be accessed via the website of the World Medical Association at http://www.wma.net/e/policy/17-c_e.html.

13 Study Management and Regulatory Affairs

13.1 Multicenter guidelines

The specific responsibilities of the Lead Investigator and the Coordinating Center are presented in Appendix B. Clinical studies coordinated by The University of Chicago must be conducted in accordance with the ethical principles that are consistent with Good Clinical Practices (GCP) and in compliance with other applicable regulatory requirements

The Study Lead Investigator/Coordinating Center is responsible for distributing all official protocols, amendments, and IND Action Letters or Safety Reports to all participating institutions for submission to their individual IRBs for action as required.

13.2 Institutional Review Board (IRB) Approval and Consent

Before implementing this study, the protocol, the proposed informed consent form and other information to subjects, must be reviewed by a properly constituted Institutional Review Board/Independent Ethics Committee (IRB/IEC/REB). A signed and dated statement that the protocol and informed consent have been approved by the IRB/IEC/REB must be given to Novartis before study initiation. The name and occupation of the chairman and the members of the IRB/IEC/REB must be supplied to Novartis. Any amendments to the protocol, other than administrative ones, must be approved by this committee.

Unless otherwise specified, each participating institution must obtain its own IRB approval. It is expected that the IRB will have the proper representation and function in accordance with federally mandated regulations. The IRB should approve the consent form and protocol.

In obtaining and documenting informed consent, the investigator should comply with the applicable regulatory requirement(s), and should adhere to Good Clinical Practice (GCP) and to ethical principles that have their origin in the Declaration of Helsinki.

Before recruitment and enrollment onto this study, the patient will be given a full explanation of the study and will be given the opportunity to review the consent form. Each consent form must include all the relevant elements currently required by the FDA Regulations and local or state regulations. Once this essential information has been provided to the patient and the investigator is assured that the patient understands the implications of participating in the study, the patient will be asked to give consent to participate in the study by signing an IRB-approved consent form.

Prior to a patient's participation in the trial, the written informed consent form should be signed and personally dated by the patient and by the person who conducted the informed consent discussion.

The treating investigator (or their designee) must explain to each subject (or legally authorized representative) the nature of the study, its purpose, the procedures involved, the expected duration, the potential risks and benefits involved and any discomfort it may entail. Each subject must be informed that participation in the study is voluntary and that he/she may withdraw from the study at any time and that withdrawal of consent will not affect his/her subsequent medical treatment or relationship with the treating physician.

This informed consent should be given by means of a standard written statement, written in non-technical language. The subject should read and consider the statement before signing and dating it, and should be given a copy of the signed document. If the subject cannot read or sign the documents, oral presentation may be made or signature given by the subject's legally appointed representative, if witnessed by a person not involved in the study, mentioning that the patient could not read or sign the documents. No patient can enter the study before his/her informed consent has been obtained.

The informed consent form is considered to be part of the protocol, and must be submitted by the site investigator with it for IRB/IEC/REB approval.

Fertile men and women of child bearing potential should be informed that taking the study medication may involve unknown risks to the fetus if pregnancy were to occur during the study and agree that in order to participate in the study they must adhere to the contraception requirement as outlined in this protocol for the duration of the study. If there is any question that the patient will not reliably comply, they should not be entered in the study

13.3 Food and Drug Administration (FDA) Approval

This study will be conducted under an IND held by **[name]** at the University of Chicago. The University of Chicago CCTO will be responsible for facilitating all communications with the FDA on behalf of the IND holder. Participating sites should not communicate directly with the FDA.

13.4 Required Documentation

Prior to the selection of a study site that is not a full member of the Personalized Cancer Care Consortium, the audit and trial oversight processes for the site must be reviewed and approved by the UC CCC Clinical Research Advisory Committee.

Before the study can be initiated at any site, the following documentation must be provided to the Cancer Clinical Trials Office (CCTO) at the University of Chicago Comprehensive Cancer Center.

- A copy of the official IRB approval letter for the protocol and informed consent
- IRB membership list
- CVs and medical licensure for the principal investigator and any sub-investigators who will be involved in the study.
- Form FDA 1572 appropriately filled out and signed with appropriate documentation
- CAP and CLIA Laboratory certification numbers and institution lab normal values
- Investigational drug accountability standard operating procedures
- Additionally, before the study can be initiated at any site, the required executed research contract/subcontract must be on file with the University of Chicago.

13.5 Data and Safety Monitoring

This study will be remotely monitored by the designated University of Chicago Clinical Research Associate (CRA) in accordance with the University of Chicago, Section of Hematology/Oncology standard operating procedure titled Monitoring of Multi-Institutional Investigator Initiated Clinical Trials.

Prior to subject recruitment, and unless otherwise specified, a participating site will undergo a Site Initiation Teleconference to be conducted by the designated University of Chicago research team. The site's principal investigator and his or her study staff must attend the site initiation meeting.

Monitoring will be conducted to verify the following:

- Adherence to the protocol
- Completeness and accuracy of study data and samples collected
- Compliance with regulations
- Submission of required source documents

Participating sites will also undergo a site close-out teleconference upon completion, termination or cancellation of a study to ensure fulfillment of study obligations during the conduct of the study, and to ensure that the site Investigator is aware of his/her ongoing responsibilities.

Unless otherwise specified, this protocol will undergo weekly review at the multi-institutional data and safety monitoring teleconference as per procedures specified by the UC CCC NCI-approved Data and Safety Monitoring Plan. The conference will review:

- Enrollment rate relative to expectations, characteristics of participants
- Safety of study participants (Serious Adverse Event & Adverse Event reporting)
- Adherence to protocol (protocol deviations)
- Completeness, validity and integrity of study data
- Retention of study participants

Protocol deviations are to be documented using the Protocol Deviation Form in the eVelos clinical trial management system. Deviations that are considered major because they impact subject safety or alter the risk/benefit ratio, compromise the integrity of the study data, and/or affect subjects' willingness to participate in the study must be reported into the eVelos system within 7 days.

13.6 Auditing

In addition to the clinical monitoring procedures, the University of Chicago Cancer Clinical Trials Office (CCTO) will perform routine Quality Assurance Audits of investigator-initiated clinical trials as described in the NCI-approved UC CCC DSM Plan. Audits provide assurance that trials are conducted and study data are collected, documented and reported in compliance with the protocol. Further, they ensure that study data are collected, documented and reported in compliance with Good Clinical Practices (GCP) Guidelines and regulatory requirements by performing annual quality assurance audits. The CCTO will review subjects enrolled at the University of Chicago and at institutions who are formal members of the Personalized Cancer Care Consortium (PCCC) in accordance with audit procedures specified in the Data and Safety Monitoring plan.

Auditing procedures for participating sites that are not full members of the PCCC must be specified and approved by the UC CCC Clinical Research Advisory Committee. In general, for sites that are not full members of the PCCC, auditing responsibility will be delegated to the participating center, with the annual audit report forwarded to the University of Chicago for review.

A regulatory authority (e.g. FDA) may also wish to conduct an inspection of the study, during its conduct or even after its completion. If an inspection has been requested by a regulatory authority, the site investigator must immediately inform the University of Chicago Cancer Clinical Trials Office and Regulatory Manager that such a request has been made.

